## STATISTICAL ANALYSIS PLAN

Sleeping disturbance	X/XX (X.X)							
Laboratory abnormalities, n/N (%)	X/XX (X.X)							
Creatinine	X/XX (X.X)							
Total bilirubine	X/XX (X.X)							
Alkaline phosphatase	X/XX (X.X)							
Alanyl transfarase (ALT)	X/XX (X.X)							
Aspartate transfarase (AST)	X/XX (X.X)							

QTc: QT corrected using Bazett's formula. Adverse event grading: grade 1: mild; grade 2: moderate; grade 3: severe; grade 4: potentially life-threatening

Incidence of QTc abnormalities (>500 milliseconds) and bradycardia is defined as a subjects experience these abnormalities at one or more timepoints.

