Whether this 'mutual exclusiveness' represents a role of *pfmdr1* in piperazine resistance (for instance by restricting the amount of piperazine entering the food vacuole) or is simply the effect of a relative low mefloquine pressure in the last decade in Cambodia and Vietnam needs further investigation. Importantly, although in low frequency, parasites bearing both markers of mefloquine resistance and piperazine resistance (*pfmdr1* and *pfplasmepsin2-3* amplification, respectively) have been found in field isolates [16], and its prevalence was recently reported to have increased in Preah Vihear province in Cambodia, after the reintroduction of artesunate-mefloquine as first line treatment [17]. The consequence of the double amplification of *pfmdr1* and *pfplasmepsin2-3* for efficacy of the TACT DHA-piperazine-mefloquine has not been established.

An increase in the QTc-interval following intake of the antimalarials piperazine and amodiaquine has been described [18-22]. In the recent TRACII study conducted primarily in adults, we also observed that the QTc interval increased after administration of DHA-piperazine by a mean of around 20 milliseconds. Reassuringly, the addition of mefloquine to DHA-piperazine did not lead to a further increase of the QTc-interval. Further, the incidence of a QTc prolongation following treatment of more than 60 milliseconds was comparable between subjects treated with DHA-piperazine and DHA-piperazine + mefloquine. Data from the TRACII study also confirmed that a treatment with artemether-lumefantrine does not prolong the QTc-interval whereas the addition

of amodiaquine to artemether-lumefantrine prolonged the QTc-interval by about 10 milliseconds over the first 64 hours, which conforms to what has been previously described for amodiaquine. Amodiaquine did not increase the incidence of a QTc-prolongation >60 milliseconds above baseline, which is rare in the treatment with artemether-lumefantrine alone (about 1 in 300 treatments). Any antimalarial treatment is associated with a drop in the heart rate in the first day of treatment. As the fever and/or clinical illness subsides the heart rate generally decreases. The TRACII study confirmed previous findings that amodiaquine use is associated with a bigger decrease in heart rate compared to other antimalarials and a higher incidence of bradycardia (<54 beats/minute), both in adults and children.

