12. SAFETY REPORTING

This trial will use drugs that have either been registered or evaluated extensively.

To allow for comparison of safety and tolerability of both new TACTs compared to the ACTs we will record and review all Adverse Events (AEs) and Serious Adverse Events, (SAEs) that occur in the study.

A symptom questionnaire will be performed daily during hospitalisation and at each subsequent visit to the health care facility, to aid in the identification of adverse events. An additional questionnaire will be administered to subjects who report psychological symptoms.

The investigator is responsible for the detection and documentation of events meeting the criteria and definition of an adverse event (AE) or serious adverse event (SAE), as provided in this protocol.

All SAEs and AEs will be promptly documented from the moment of randomisation in the study to discontinuation of the patient from study participation. Any events occurring between screening and randomization will be considered as baseline, pre-existing conditions. Any conditions that were present at baseline will not be considered adverse events unless the grade of the condition deteriorates.

Each adverse event will be graded according Common Terminology Criteria for Adverse Events

(CTCAE) version 5.0, adapted for paediatric populations where needed:

https://ctep.cancer.gov/protocolDevelopment/electronic_applications/ctc.htm#ctc_50

All adverse events must be recorded in the AE /SAE CRF. To avoid colloquial expressions, the adverse event should be reported in standard medical terminology. If a definitive diagnosis is possible, then it should be recorded. Whenever possible, the aetiology of the abnormal findings will be documented on the CRF. Any additional relevant laboratory results obtained by the Investigator during the course of this study will be recorded on the CRF.

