**STATISTICAL ANALYSIS PLAN**

Total Bilirubin (µMol/L): median (IQR)	XX.X (XX.X- XX.X)	XX.X (XX.X- XX.X)	XX.X (XX.X- XX.X)	XX.X (XX.X- XX.X)	XX.X (XX.X- XX.X)
Alkaline Phosphatase (IU/L): median (IQR)	XX.X (XX.X- XX.X)	XX.X (XX.X- XX.X)	XX.X (XX.X- XX.X)	XX.X (XX.X- XX.X)	XX.X (XX.X- XX.X)
QT interval on monitor (milliseconds): median (IQR)	XX.X (XX.X- XX.X)	XX.X (XX.X- XX.X)	XX.X (XX.X- XX.X)	XX.X (XX.X- XX.X)	XX.X (XX.X- XX.X)
Calculated QTc Bazett interval (milliseconds): median (IQR)	XX.X (XX.X- XX.X)	XX.X (XX.X- XX.X)	XX.X (XX.X- XX.X)	XX.X (XX.X- XX.X)	XX.X (XX.X- XX.X)

**3.3 Efficacy of the ACTs and TACTs as defined by the 42-day PCR corrected adequate clinical and parasitological response (ACPR) within each individual site**

Efficacy will be reported as cumulative ACPR cure rates by day 42 estimated by day 42 PCR corrected efficacy and compared between ACT vs TACT. The Kaplan Meier/survival methods will be used to visually show time to . Non-inferiority will be assessed using 95% one side confidence intervals.

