### **3.5 Changes in the electrocardiogram (such as prolongation of the QTc-interval) in patients treated with TACT versus standard ACT**

Incidence of prolongations of the QTc-interval (QTc Bazett)>500 milliseconds at least once (at H4, H48, H52) will be summarized in table 5. Absolute changes in the QTc-interval will be summarized as in tables 8, and will be graphically displayed by arm as in figure 5. Comparisons on the changes in the QTc-interval will be made using the unpaired t-test for each specific time point.

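### Bazett is the only QT correction the SAP names, so if QT scales with RR to a power below 0.5, amodiaquine's extra heart-rate slowing could hide part of its QTc effect; add Fridericia and heart-rate change by arm

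*SAP*

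**What the plan says.** The SAP names a QT correction in three places, and each time it is Bazett: the baseline QTc row of Table 1, section 3.5, and the Table 6 footnote ("QTc: QT corrected using Bazett's formula"). For the threshold count, section 3.5 says "Incidence of prolongations of the QTc-interval (QTc Bazett)>500 milliseconds at least once (at H4, H48, H52) will be summarized in table 5". For the change in QTc it says "Comparisons on the changes in the QTc-interval will be made using the unpaired t-test for each specific time point". Table 8 lays out QTc and its change from H0 by arm and names no formula of its own.

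Neither document gives a second correction, a heart-rate term or a sensitivity analysis for QTc. Heart rate and uncorrected QT each have a row in Table 1 and none in the post-dose tables. The Table 6 footnote mentions bradycardia, but the table as available to us shows no row for it.

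Protocol 3.1 says heart rate drops on the first day of any antimalarial treatment ("As the fever and/or clinical illness subsides the heart rate generally decreases"). From the TRACII study it adds that "amodiaquine use is associated with a bigger decrease in heart rate compared to other antimalarials", with more bradycardia, in adults and children. The same section puts the QTc effect of adding amodiaquine to AL at about 10 ms over the first 64 hours, without saying which correction was used.

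**The concern.** A QT correction is meant to remove heart rate from the comparison. Bazett divides QT by the square root of RR. If QT in these patients depends on RR less steeply than that, Bazett QTc still contains heart rate and falls when the rate falls.

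The protocol expects amodiaquine itself to slow the heart more than other antimalarials do. The correction is then mixed up with the drug under test. The slowing happens after randomisation and in one arm more than the other, so randomisation gives no protection, and the error runs towards reassurance. Protocol 3.2 says the low incidence of QTc prolongation seen so far comes from a relatively small population and needs confirmation. A bias of a few milliseconds matters when the effect being checked is of the order of 10 ms.

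There is a second consequence. Most sites enrol only children under 12, all with fever or recent fever. At high heart rates a Bazett value above 500 ms can arise from a less extreme underlying QTc, which would add noise to the threshold count in every arm.

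**Working it through.** The plan states no figure for this effect, so there is nothing to reproduce. The check is algebra with assumed inputs.

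**Inputs.** From the documents: the Bazett correction (SAP Table 1, 3.5, Table 6), the direction of the heart-rate change (protocol 3.1) and the effect of about 10 ms (protocol 3.1). Assumed: the exponent b linking QT to RR, a rate-free corrected QT c of 400 ms, and all heart rates.

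**Formula.** If QT = c × RR^b with RR = 60/HR, then QTcB = QT/RR^0.5 = c × (HR/60)^(0.5 − b). For b < 0.5 this falls as HR falls, at b = 0.5 it does not depend on HR, and for b > 0.5 it rises as HR falls.

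**Between arms.** AL+placebo is taken at 100 bpm and AL+AQ at 95 or 90 bpm, with c = 400 ms in both. For b = 1/3: 400 × (100/60)^(1/6) = 435.5; at 95 bpm, 431.8; at 90 bpm, 428.0. Differences below are from unrounded values; a minus sign means the effect is exaggerated.

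| b | 100 bpm | 95 bpm | 90 bpm | hidden at 95 | hidden at 90 |
|---|---|---|---|---|---|
| 1/3 | 435.5 | 431.8 | 428.0 | 3.7 | 7.6 |
| 0.40 | 421.0 | 418.8 | 416.6 | 2.2 | 4.4 |
| 0.50 | 400.0 | 400.0 | 400.0 | 0 | 0 |
| 0.55 | 389.9 | 390.9 | 392.0 | −1.0 | −2.1 |

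**With a true effect of 10 ms added.** Set c = 410 in AL+AQ and b = 1/3. At 95 bpm, 410 × (95/60)^(1/6) = 442.6, so the difference reads 442.6 − 435.5 = 7.1 ms. At 90 bpm it reads 3.1 ms. The shortfalls (2.9 and 6.9 ms) are a little smaller than in the table because Bazett also stretches the 10 ms itself, by a factor of about 1.08 at 95 bpm.

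Over a wider grid (AL+placebo rates 130→100, 110→85 and 90→70 bpm; extra fall with amodiaquine 3, 5 or 10 bpm):
- b = 0.25 to 0.40: bias from −0.8 to −15.7 ms
- b = 0.50: bias 0
- b = 0.55: bias from +0.4 to +3.1 ms

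**Within an arm.** On the same three heart-rate paths, with b = 1/3 and no drug effect, AL+placebo shows a change from H0 of −17.6 to −19.5 ms. This part cancels between arms, but it sits in the change column of Table 8.

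**Threshold.** Bazett reaches 500 ms at a true QTc of 500/(HR/60)^(0.5 − b). At b = 1/3 that is 459 ms at 100 bpm, 445 ms at 120 bpm and 434 ms at 140 bpm. At 120 bpm it is 420 ms for b = 0.25, 467 ms for b = 0.40 and 500 ms for b = 0.50.

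**What Fridericia adds.** QTcF = c × (HR/60)^(1/3 − b). At b = 1/3 it is free of rate. At b = 0.40 it errs the other way: 386.6 ms at 100 bpm, 387.9 at 95 and 389.3 at 90, so the slower arm reads 1.3 or 2.7 ms too high. For exponents between 1/3 and 0.5 the rate biases of the two corrections have opposite signs, which is why showing both is more useful than replacing one with the other.

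**The case against.** The strongest reply is that the documents do not show that Bazett is wrong for these patients. They give no QT–RR exponent, no mean heart-rate change and no time point for the extra amodiaquine fall. At 0.5 there is no bias, and above it Bazett would exaggerate the amodiaquine effect. This stands. A reader might infer that the AL+AQ effect is understated and that tachycardic children are over-flagged; the documents support only that both could happen.

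The 10 ms is also a loose yardstick. If TRACII used Bazett, that figure already contains any rate artefact, and subtracting the table's values from it would count the artefact twice. It is used here only for scale.

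Much of the fall in heart rate is common to both arms and cancels in the randomised comparison. That is right for the fever-related part and not for the extra amodiaquine part. Inflation of the threshold count also affects all arms, and for b < 0.5 the slower rate in AL+AQ would lower that arm's count.

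QTc safety does not rest on Bazett alone. The secondary endpoint and the protocol's SAE rule use QT or QTc above 500 ms, and protocol 14.1 plans a concentration–QTc analysis. But the automated reading in 9.6 and that analysis name no formula, and the SAP's post-dose tables show no uncorrected QT. So over-flagging cannot be claimed for the 9.6 trigger, and the concentration analysis cannot be counted as a safeguard.

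A reader might also infer that a child already above 500 ms before dosing is counted as an event, because the Table 6 footnote refers to one or more time points without mentioning H0. The documents do not support this. Section 3.5 and the Table 6 row list post-dose times only, and SAP 3.4 limits adverse event summaries to events that are new or have increased in intensity. Protocol 12 agrees: "Any conditions that were present at baseline will not be considered adverse events unless the grade of the condition deteriorates".

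**Conclusion.** The point holds conditionally. Bazett is the only correction the SAP names, the protocol itself expects more slowing with amodiaquine, and the planned tables would not let a reader separate a small true QTc effect from a rate artefact. If the exponent is below 0.5, the AL+AQ minus AL+placebo difference is biased downward. Under the assumed values above, that ranges from under 1 ms to more than the whole 10 ms. At 0.5 the bias is nil, and above 0.5 it changes sign. The within-arm changes from H0 are open to a larger distortion, which does not carry over to the comparison between arms. The weakness is relying on one untested exponent when the recorded data allow it to be checked.

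**What to change.** In SAP 3.5 and Tables 6 and 8:

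1. Report the change in QTc and the count above 500 ms with Fridericia beside Bazett. Optionally, add a sensitivity analysis with an exponent fitted to the pre-dose H0 ECGs, noting that it is extrapolated to lower post-treatment rates.
2. Report heart-rate change from H0 by arm at each ECG time. Protocol 9.6 sets the late inpatient ECG at H64 for AL arms, whereas the threshold count in SAP 3.5 lists H4, H48 and H52; these lists must be reconciled for the AL comparison to be read.
3. State which formula lies behind the automated reading in protocol 9.6.

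Patients above 500 ms at H0 should not be removed from the count by a separate rule. The treatment-emergent rule in SAP 3.4 already governs and keeps a patient who worsens from such a value.

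The cost is SAP wording, recomputation from QT and heart rate (both needed for any Bazett value), an extra QTc column and a heart-rate row. No ECG is added and no clinical action changes.

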**Table 7a Proportions of patients that report a full course of observed TACT or ACT**

	AL, n/N (%), 95% CI)	A+AQ, n/N (%), 95% CI)	ASMQ, n/N (%), 95% CI)	ASMQ + PPQ, n/N (%), 95% CI)	p-value (AL vs AL+AQ)	p-value (ASMQ vs ASMQ+PPQ)
Completing full course of study drug	XXXX/XXXX (XX.X, XX.X - XX.X)	0.XXX	0.XXX			

**Table 7b. Necessity for retreatment due to vomiting or spitting study drug**

	AL+AQ	AL+Placebo	ASMQ+PPQ	ASMQ+Placebo
Number of participants	XX	XX	XX	XX
Number of total doses	XX	XX	XX	XX

## STATISTICAL ANALYSIS PLAN

Retreatment events				
Number of participants	XX	XX	XX	XX
Retreatment events due to vomiting (< 30 min) only†	X(X)	X(X)	X(X)	X(X)
Retreatment events due to spitting only†	X(X)	X(X)	X(X)	X(X)
Both vomit and spitting*†	X(X)	X(X)	X(X)	X(X)
Total number of retreatments†	X(X)	X(X)	X(X)	X(X)
Total number of participants vomiting after retreatment (< 60 min) or rescue therapy given	X(X)	X(X)	X(X)	X(X)
Number of participants vomiting after retreatment (< 60 min)	X(X)	X(X)	X(X)	X(X)
Number of rescue treatments given	X(X)	X(X)	X(X)	X(X)

**Table 8 QTc-intervals and changes in QTcintervals over time (relevant time points only will be summarised)**

Time-point	AL+Placebo			AL+AQ			ASMQ+Placebo			ASMQ+PPQ		
	QTc	Δ-QTc	p-value									
H0	XXX.X (XX.X)	Baseline	Baseline									
H4	XXX.X (XX.X)	XX.X (XX.X)	0.XXX									
H24	XXX.X (XX.X)	XX.X (XX.X)	0.XXX									
H28	XXX.X (XX.X)	XX.X (XX.X)	0.XXX									
H48	XXX.X (XX.X)	XX.X (XX.X)	0.XXX									

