7. PROPOSED ACTIVITIES

Subjects will be randomized to up to four arms: artemether-lumefantrine + amodiaquine, artemether-lumefantrine + placebo, artesunate-mefloquine + piperazine and artesunate-mefloquine + placebo. As a contingency measure in case of significant differences in the efficacy or safety of one of the combinations being tested and/or study drug expiry or unavailability, subjects may be randomized to 2 arms with a matching ACT-TACT pair, i.e., with artemether-lumefantrine + placebo or artemether-lumefantrine + amodiaquine OR artesunate-mefloquine + placebo or artesunate-mefloquine + piperazine.

Some sites may randomize between 2 arms only with matching ACT-TACT pairs, i.e., artemether-lumefantrine + placebo or artemether-lumefantrine + amodiaquine OR artesunate-mefloquine + placebo or artesunate-mefloquine + piperazine. In Rwanda, subjects will be randomized between 2 arms consisting of artemether-lumefantrine + placebo or artemether-lumefantrine + amodiaquine.

In the control arms, the ACT will be co-packed with a matched (appearance) placebo.

In lower transmission settings (Annual Parasite Incidence <50 per 1000 population per year) the treatment will include a single 0.25 mg/kg gametocytocidal dose of primaquine as recommended by the WHO for children ≥ 10 kg. All drug administrations will be observed.

Subjects will be treated in an in-patient unit for 3 days and followed up weekly up to D63. Microscopy to detect and quantify malaria parasitaemia will be performed daily (more frequently in patients with parasite density of $>5000/\mu\text{L}$ at inclusion) during hospitalization, at all weekly and unscheduled visits. A physical examination and measurements of vital signs along with a symptom questionnaire for tolerability will be performed and recorded through a standardized method at baseline, daily during admission and weekly during follow up through D42 and at all unscheduled visits. Physical exam, vital sign measurements and assessments of symptoms will be performed on D49, D56, and D63 only for patients who are parasitaemic or those who report fever or other symptoms. Electrocardiographs will be performed during admission (H0, H4, H52 or H64) and day 42 of follow up to assess and compare the effect of ACTs and TACTs antimalarials on QT or QTc intervals.

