9.6. Electrocardiographic recording

Electrocardiograms (ECGs) will be recorded at D0H0, D0H4, D2H52 (for treatments containing ASMQ) or D2H64 (for treatments containing AL) and D42 in order to assess changes in the QT/QTc interval.

At the timepoint D0H4 and D2H52/D2H64 an abnormal automated electronic reading (QT or QTc-interval > 500 milliseconds) will be considered a Serious Adverse Event and will lead to discontinuation of the study drug but not discontinuation of the patient from the trial. A specific work instruction will describe procedures such as identifying other causes of QT/QTc prolongation, study drug replacement and follow up of the QT/QTc interval until normalization.

QT/QTc intervals will be measured every six hours after the first abnormal QT/QTc interval is recorded until the QT/QTc interval has normalized in two consecutive ECGs.

Additional blood samples will be taken for pharmacological measurements at the moment of the identification of the abnormal QT/QTc interval and 6 and 12 hours after the first identification of the abnormal QT/QTc interval in order to assess the correlation between the prolonged QT/QTc interval and the drug levels that could be leading to the prolonged QT/QTc interval.

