9.7.5. Blood sampling for pharmacokinetics

PK sampling (1 ml whole blood in heparin per sampling occasion). Venous plasma will be used to evaluate the drug exposures to antimalarial drugs used in this study (E.g. artesunate, artemether, lumefantrine, amodiaquine, piperazine, mefloquine, and their metabolites). A work instruction will be written to detail the technique for specimen collection, handling and storage. Samples will be centrifuged immediately and the plasma stored frozen at minus 80°C or lower in properly labelled cryotubes.

A maximum of seven samples for PK/PD analyses will be collected in each patient over a total sampling period of 42 days:

- One fixed day 0 sample will be collected for lumefantrine, amodiaquine, piperaquine, and mefloquine (and their metabolites) concentration measurements in all subjects.
- One sample will be collected systematically at the same time as the ECG at H52 (for ASMQ containing arms) and H64 (for AL containing arms)
- One fixed day 7 sample will be collected for lumefantrine, amodiaquine, piperaquine, and mefloquine (and their metabolites) concentration measurements in all subjects
- Two samples at random time-points during the first 3 days of dosing will be collected for artemether, artesunate, lumefantrine, amodiaquine, piperaquine, and mefloquine (and their metabolites) concentration measurements in 500 patients
- Two samples within random time windows during the 42 days of follow up will be collected for lumefantrine, amodiaquine, piperaquine, and mefloquine (and their metabolites) concentration measurements in 500 patients.
- In Niger only – three random samples during the first 3 days of dosing will be collected for artemether, artesunate, lumefantrine, amodiaquine, piperaquine, and mefloquine (and their metabolites) concentration measurements in all patients

Additional PK blood samples will be collected in the following situations:

- In case of an abnormal QT/QTc interval at H4, D42. A blood sample will be obtained at the moment of the first identification of the abnormal QT/QTc interval.
- At 6 and 12 hours after the first abnormal QT/QTc interval at any time-point (H4, H52, H64, D42) in order to assess the correlation between the prolonged QT/QTc interval and the drug levels that could result in a prolonged QT/QTc interval (maximum 3 ml heparin blood).
- In case of a recurrent infection at the day of recurrence (1 ml heparin blood).

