12.1.4. Study defined SAEs

For the purpose of this study, the following are considered SAEs

- Prolongation of the QT or QTc interval to >500 milliseconds
- AST/ALT >10 times ULN
- ALT or AST >3 times ULN with Total Bilirubin >2 times ULN (Hy's Law)
- Creatinine >3.5 times ULN

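### The protocol schedules a day-42 ECG in all subjects to compare ACTs and TACTs on QT/QTc, but the SAP plans no between-arm QTc analysis at day 42, and its other ECG time points do not match the schedule

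*SAP*

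**What the plan says.** **Schedule and purpose.** Protocol section 7 plans ECGs during admission (H0, H4, and H52 or H64) "and day 42 of follow up to assess and compare the effect of ACTs and TACTs antimalarials on QT or QTc intervals". Section 9.6 repeats the schedule, with H52 for ASMQ arms and H64 "for treatments containing AL) and D42 in order to assess changes in the QT/QTc interval". Neither section limits the day-42 ECG to a subset.

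**Endpoints.** Protocol 5.2 and SAP 2.1.3 define a safety endpoint of QT or QTc above 500 ms at H4, at H52/H64 and between them. SAP 2.1.3 also lists a general endpoint, change in the electrocardiogram under TACT versus standard ACT, with no time point attached.

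**Analysis.** SAP 3.5 counts QTc above 500 ms at H4, H48 and H52. The matching row in SAP Table 6 names H4 and H48/H52. QTc changes are to be compared by unpaired t-test at each time point and shown in Table 8, "QTc-intervals and changes in QTcintervals over time (relevant time points only will be summarised". The rows of Table 8 run from H0 to H64.

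**SAE wording.** Section 9.6 states: "At the timepoint D0H4 and D2H52/D2H64 an abnormal automated electronic reading (QT or QTc-interval > 500 milliseconds) will be considered a Serious Adverse Event". Section 12.1.4 lists "Prolongation of the QT or QTc interval to >500 milliseconds" with no time point.

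**The concern.** Day 42 is the only scheduled ECG after the treatment phase. It is therefore the only one that can show whether an early QTc difference between matching arms has gone once treatment is over. The question matters to this trial: Protocol 3.2 says that the earlier reassuring QTc data come from a relatively small population and need confirmation. Protocol 3.1 reports QTc increases of about 10 ms when amodiaquine was added to AL and about 20 ms after DHA-piperaquine.

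Followed as written, the SAP would leave undone a comparison that the protocol gives as a reason for recording the ECG. If it were added after unblinding, the choice of time point, reference and test would be post hoc.

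The 500 ms count has a different fault. Read literally, it leaves out the late treatment-phase ECG of both AL arms, so AL and AL+AQ would be judged on the H4 recording plus a time at which no ECG is scheduled.

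**Working it through.** **Step 1: time points side by side.**

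| Time | ECG scheduled (Protocol 7, 9.6) | In the >500 ms endpoint (Protocol 5.2, SAP 2.1.3) | In the >500 ms count (SAP 3.5, Table 6) | Row in SAP Table 8 |
|---|---|---|---|---|
| H0 | yes | no | no | yes |
| H4 | yes | yes | yes | yes |
| H24, H28 | no | only as an in-between time | no | yes |
| H48 | no | only as an in-between time | yes | yes |
| H52 | yes, ASMQ arms | yes | yes | yes |
| H60 | no | only as an in-between time (AL arms) | no | yes |
| H64 | yes, AL arms | yes | **no** | yes |
| Day 42 | yes | no | no | **no** |

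Two mismatches follow. Day 42 is scheduled with a comparative purpose but has no QTc output. H64 is scheduled and inside the endpoint but is missing from the count, while H48 is counted without a scheduled ECG.

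**Step 2: number of day-42 ECGs affected.** From Protocol 2 and 15.1:

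- Planned enrolment: 7 × 432 + 216 = 3,240.
- AL pair, eight sites: 8 × 72 = 576 ACT and 8 × 144 = 1,152 TACT (Rwanda's 216 split 1:2).
- ASMQ pair, seven sites: 7 × 72 = 504 ACT and 7 × 144 = 1,008 TACT.
- The plan inflates 60 to 72 and 120 to 144. If the whole inflation is lost, 480 and 960 remain in the AL pair, and 420 and 840 in the ASMQ pair, 2,700 in all.

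**Step 3: precision of a day-42 comparison.** The documents give no SD for QTc change. I assume 25 ms and show 20 to 30 ms. SE = SD × √(1/n₁ + 1/n₂).

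- AL pair: √(1/480 + 1/960) = 0.0559. SE = 1.12, 1.40 and 1.68 ms at SD 20, 25 and 30. The 95% half-width (1.96 × SE) is 2.2, 2.7 and 3.3 ms.
- ASMQ pair: √(1/420 + 1/840) = 0.0598. SE = 1.20, 1.49 and 1.79 ms. The half-width is 2.3, 2.9 and 3.5 ms.
- If instead 20% of those enrolled are lost (about 461/922 and 403/806), the largest SE is 1.83 ms and the largest half-width 1.96 × 1.83 = 3.6 ms.

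**Step 4: what could be excluded.** If the true difference is zero, the effect that can be excluded with 80% power is (1.96 + 0.84) × SE. At SD 25 this is 2.80 × 1.40 = 3.9 ms (AL pair) and 2.80 × 1.49 = 4.2 ms (ASMQ pair), so about 4 ms.

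**Step 5: SAE wording.** Section 9.6 names H4 and H52/H64 and says nothing about day 42. Section 12.1.4 sets no time. Section 9.7.5 provides for extra drug-level samples "after the first abnormal QT/QTc interval at any time-point (H4, H52, H64, D42", so the protocol foresees an abnormal day-42 reading. The day-42 visit may fall on days 41 to 44 (Protocol 9.9), whereas Table 6 covers the first 42 days, so the window adds to the uncertainty about where such a reading would be counted.

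**The case against.** **The Table 8 caption allows for this.** It limits the summary to relevant time points, so surplus rows are harmless shells. That is fair for the surplus rows: they matter little if left empty. It does not cover day 42. The caption lets listed rows be dropped; it does not add one that is not listed.

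**Day 42 is outside the 500 ms endpoint.** This stands. Protocol 5.2 and SAP 2.1.3 both restrict that endpoint to H4 through H52/H64, so a reader who takes the absence of day 42 from the 500 ms count as an error would be wrong. The gap is against the stated purpose of the ECG and the general ECG-change endpoint. The same definition is what makes the omission of H64 a fault.

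**The recordings are not wasted.** A reader might infer that the day-42 ECGs go unused. The documents do not support that. Protocol 14.1 relates predicted drug levels at the times of QTc measurement to QTc without excluding day 42, SAP 3.7 defers PK/PD work to a separate plan, and SAP 3.4 says that clinically relevant abnormalities will be described. What is missing is a between-arm analysis.

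**Section 9.6 contradicts section 12.1.4.** This too is tempting, but 9.6 never says that a day-42 reading is not an SAE, and both sections can be followed together. It is an unclear scope, not a contradiction.

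**Day 42 is not a clean convalescent reference.** This stands. Under Protocol 9.5.5, subjects with recurrent infection stay in follow-up and may be retreated with the same or another ACT. Some day-42 ECGs may therefore follow a second illness or renewed exposure, and possibly not equally by arm.

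**Conclusion.** The point holds as a mismatch between the SAP and the protocol's ECG schedule, and it should be corrected. Between 2,700 and 3,240 planned day-42 ECGs have no planned between-arm QTc analysis, and the 500 ms count omits the late ECG of the AL arms.

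The comparison would be informative. A 95% half-width of about 3 ms is small beside the 10 to 20 ms increases cited in the protocol, and a persistent effect of about 4 ms could be excluded with 80% power at SD 25. It would be too strong to say that 3 ms could be excluded, because that treats the half-width as power. With a true difference of zero, the chance that the upper limit falls below 3 ms is Φ(3/SE − 1.96), about 57% in the AL pair and 52% in the ASMQ pair.

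These figures assume an SD of QTc change of 20 to 30 ms, full recruitment with all four arms at seven sites, and a readable ECG from every subject seen at day 42. The mismatch itself rests on none of them. The SAE wording is a separate and smaller matter: the status of a day-42 reading is unclear.

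**What to change.** 1. In SAP Table 8, add a day-42 row giving QTc, change from H0, and the between-arm difference with 95% CI for each matching pair. Remove H24, H28, H48 and H60, where no ECG is scheduled.
2. In SAP 3.5 and the Table 6 row, count QTc above 500 ms at H4 and at H52/H64. Repeat ECGs taken between those times stay in, as the endpoint already provides. Correct the cross-reference in SAP 3.5 as well: it sends the count to Table 5, which holds day-63 efficacy.
3. If day 42 is used as a convalescent reference for H4 and H52/H64, label that analysis supplementary and repeat it without subjects retreated for recurrence before day 42.
4. The sponsor should reconcile Protocol 9.6 with 12.1.4 on a day-42 reading above 500 ms, and state how a visit on days 43 or 44 is handled in Table 6, so that sites count alike.

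No new data are needed. The cost is one added table row, edited time-point labels, a short supplementary analysis and a one-line protocol clarification, all best done before unblinding.
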